4.2 Secondary Objectives

Delayed and sustained effects. A secondary objective will be to determine whether the proportion of community ambulators differs between the PUSH and PULSE interventions at 40 weeks post-randomization and, for the subset of participants who were followed for 40 weeks, whether the difference in proportions at 40 weeks changed from the difference in proportions at 16 weeks.

Effect on secondary and tertiary outcomes. There are five variables (endurance, dynamic balance, walking speed, quadriceps strength, and lower extremity function) that are hypothesized to be precursors to community ambulation. To gain a better understanding of the interventions' mechanisms, the two groups will be compared at 16 weeks post-randomization on each of these outcomes and at 40 weeks post-randomization for the subset of participants who are followed for 40 weeks. In addition, this study will assess the effect of the interventions on several tertiary outcomes including ADLs, balance confidence, quality of life, physical activity, lower extremity physical performance, depressive symptoms, increase of ≥ 50 meters in distance walked in six minutes, cognitive status, and nutritional status.

Cost-effectiveness of the interventions. The economic value of the interventions will be determined by assessing the impact on QALYs, cost, and cost per QALY gained over the follow-up period. This RCT will provide critical information on whether the specific PUSH intervention can improve a hip fracture patient's ability to ambulate in the community in a cost-effective manner compared to the non-specific PULSE intervention. To address the economic value of trial interventions versus usual care, a model-based analysis that combines trial data with other data sources also will be undertaken.

Section 5: Background

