10.3.6 Cost Effectiveness: Health Care Utilization

Resource utilization will be tracked every four weeks via telephone interview and unit costs will be assigned to each resource for which data are obtained. Resource use will reflect health care use (including both formal and informal care) since the last telephone interview. This interview will be patterned after that used in the NIH-sponsored Spine Patient Outcomes Research Trial (SPORT).¹⁶⁶ In addition to caregiver costs, the questionnaire will document other resource use including hospitalizations, other care facilities, health care visits, and diagnostic tests. As in SPORT, a health diary will be provided to each participant to assist them in accurately recording health care encounters and use of health services.

Effectiveness will be assessed in the QALY framework where health state values will be used to reflect the desirability for health outcomes on a scale from 0 (worst imaginable health state) to 1 (best imaginable health state). To estimate QALYs, health state values will be obtained using the SF-6D health state classification system,¹⁶⁷ which defines health states using participant responses to the SF-36 (described below). QALYs estimated using SF-6D are consistent with recommendations to use societal values in economic evaluations in health and medicine.¹³⁶ Although current SF-6D scoring uses preference weights from a UK population, use of the SF-6D will facilitate the planned model-based comparison between trial interventions and usual care, because several BHS investigations have utilized SF-36 in similar hip fracture populations.

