15.2.3 Cost-Effectiveness of Interventions

To assess the cost-effectiveness of study interventions, the EEC will conduct analyses of within-trial comparisons for the economic endpoints (resource utilization/costs and SF-6D/QALYs) and will also undertake a model-based analysis that allows the economic value of both study interventions to be assessed relative to usual care. Longitudinal modeling appropriate for repeated measures data will be used to make inferences on the overall differences in cost and QALYs associated with the study interventions. The basic statistical analyses of cost and QALYs will be similar to the approach described for other study endpoints, but will be undertaken in the EEC in close collaboration with the DCC.

Statistical analyses of SF-6D will produce an estimate of the incremental QALYs associated with the PUSH intervention at each time point where SF-36 is measured. The estimated difference in QALYs attributable to the PUSH intervention will be estimated by taking a time-weighted average of the time-specific intervention effects. Statistical analyses of cost data, which will be adjusted to a constant dollar year (e.g., 2012 US dollars), will produce an estimate of the incremental costs associated with the PUSH vs. PULSE intervention.

The incremental cost-effectiveness ratio (ICER), which is defined as the net change in cost divided by the net change in effectiveness (QALYs) when interventions are ranked in order of increasing cost, is the focus of the economic analysis. When estimated as added cost per QALY gained, the ICER allows the value of interventions in hip fracture to be compared with interventions in other diseases. ICERs will be estimated using both the statistical analysis of cost and QALY data (i.e., trial-based ICER) and a model-based analysis that combines trial results with other existing data (i.e., model-based ICER). The trial-based ICER addresses the economic value of the PUSH intervention relative to the PULSE, while the model-based ICER

estimates the economic value of the study interventions relative to usual care (as described below).

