15.6.2 Secondary Aims

Delayed and Sustained Effects. Follow-up will end at 16 weeks post-randomization for those consented under version 10.0 of the protocol. We estimate that there will be approximately 150 participants (not the full 210) for whom the 40-week measure of community ambulation will be available. In addition, based on our experience to date, we estimate that the community ambulation outcome will be indeterminate for 10% of the participants at the 40-week assessment. If we assume a sample size of 150 then there is 64% power for detecting a difference of 20 percentage points at alpha = 0.05 using a two-tailed test.

Effect on Secondary and Tertiary Outcomes. Using a two-sided test with alpha=0.05, a sample of 210 patients with 6.8% loss to follow-up and 12.2% treatment noncompliance will provide

80% power to detect effect sizes of 0.46 SD at 16 weeks, which are considered moderate in size, under the assumption that noncompliers assigned to the PUSH group have an equal mean and standard deviation as patients assigned to the PULSE group. Collection of some outcome measures will end after implementation of protocol version 11.0 (see Section 11:). For these measures, we estimate that there will be approximately 160 participants (not the full 210) for whom the 16-week measure will be available. Under the same assumptions, a sample of 160 will provide 80% power to detect an effect size of 0.53 SD.

Economic Evaluation. Follow-up will end at 16 weeks post-randomization for those consented under version 10.0 of the protocol. We estimate that there will be approximately 150 participants for whom the full 40-week follow-up will be available. Assuming a mean SF-6D score of 0.62 in the PULSE group and between-subject standard deviation of 0.10 (based on unpublished data from the fourth BHS cohort study), and assuming that non-compliers assigned to the PUSH group have an equal mean and standard deviation as patients assigned to the PULSE group, a sample size of 75 per group will allow us to detect a between-group difference in means of 0.055 with 80% power and using a two-sided 0.05-level test.

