To account for the correlation between repeated measures from the same person, we will fit an unstructured variance/covariance matrix to the three time points. This model accounts for outcomes at three time points: baseline, 16 weeks, and 40 weeks post-randomization. By treating the baseline value as an outcome, we quantify mean changes in the outcome relative to baseline levels. Differences between the two groups in changes from baseline to 16 and 40 weeks post-randomization will be compared using Eq. 2 by testing $H_0: b_3=0$ and $H_0: b_4=0$ respectively using a Wald chi-square test with type-I error of 0.05. All treatment effects will be reported with their respective 95% confidence intervals.

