1.3 Cost-Effectiveness of Interventions

To assess the cost-effectiveness of study interventions, the EEC will conduct analyses of within-trial comparisons for the economic endpoints (resource utilization/costs and SF-6D/QALYs) and will also undertake a model-based analysis that allows the economic value of both study interventions to be assessed relative to usual care. Longitudinal modeling appropriate for repeated measures data will be used to make inferences on the overall differences in cost and QALYs associated with the study interventions. The basic statistical analyses of cost and QALYs will be similar to the approach described for other study endpoints, but will be undertaken in the EEC in close collaboration with the DCC.

Statistical analyses of SF-6D will produce an estimate of the incremental QALYs associated with the PUSH intervention at each time point where SF-36 is measured. The estimated difference in QALYs attributable to the PUSH intervention will be estimated by taking a time-weighted average of the time-specific intervention effects. Statistical analyses of cost data, which will be adjusted to a constant dollar year (e.g., 2012 US dollars), will produce an estimate of the incremental costs associated with the PUSH vs. PULSE intervention.

The incremental cost-effectiveness ratio (ICER), which is defined as the net change in cost divided by the net change in effectiveness (QALYs) when interventions are ranked in order of increasing cost, is the focus of the economic analysis. When estimated as added cost per QALY gained, the ICER allows the value of interventions in hip fracture to be compared with interventions in other diseases. ICERs will be estimated using both the statistical analysis of cost and QALY data (i.e., trial-based ICER) and a model-based analysis that combines trial results with other existing data (i.e., model-based ICER). The trial-based ICER addresses the economic value of the PUSH intervention relative to the PULSE, while the model-based ICER estimates the economic value of the study interventions relative to usual care (as described below).

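### As worded, the QALY rule in SAP 1.3 and Protocol 15.2.3 gives a mean SF-6D difference, not QALYs accrued over follow-up; over 40 weeks the two differ by a factor of 1.30

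*SAP*

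**What the plan says.** Protocol 10.3.6 takes QALYs from SF-6D, where "health state values will be used to reflect the desirability for health outcomes on a scale from 0" (worst) to 1 (best). The aim in Protocol 4.2 is to determine economic value by "assessing the impact on QALYs, cost, and cost per QALY gained over the follow-up period".

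The derivation is in Protocol 15.2.3 and is carried unchanged into SAP 1.3. First: "Statistical analyses of SF-6D will produce an estimate of the incremental QALYs associated with the PUSH intervention at each time point where SF-36 is measured". Then, for the difference between the arms: "QALYs attributable to the PUSH intervention will be estimated by taking a time-weighted average of the time-specific intervention effects".

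Neither document gives the weights, the time unit, the handling of baseline, a multiplication by follow-up time, or a horizon shared with costs. SAP 1.3 makes the cost per QALY ratio (ICER) the centre of the economic work. It also runs that work only if the primary outcome differs significantly, or if a listed secondary outcome differs both significantly and by a clinically meaningful amount.

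**The concern.** A utility has no time dimension. A between-group SF-6D difference at week 16 is therefore a utility difference, and an average of such differences over visits is still one. QALYs accrued over a period are the area under the utility curve with time in years. Over a horizon shorter than one year, the average is larger in magnitude than the area.

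The cost side of the ratio does accumulate: Protocol 10.3.6 collects resource use every four weeks since the previous interview, and Protocol 15.6.2 speaks of cumulative costs. As written, the numerator covers the follow-up period and the denominator is expressed per year of average difference. An analyst who follows the text would report a cost per QALY on mismatched time bases. The model-based analysis could inherit the error through whatever QALY inputs it takes from the trial.

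**Working it through.** **Inputs**
- Measurement times of 0, 16 and 40 weeks: SF-36 is listed at baseline and follow-up in Protocol 11.1 and 11.2, and SAP 1.2.2 says of its longitudinal model, "This model accounts for outcomes at three time points: baseline, 16 weeks, and 40 weeks post-randomization".
- Detectable SF-6D difference of 0.055, SD 0.10, 75 per group, 80% power, two-sided 0.05 (Protocol 15.6.2).
- Noncompliance 12.2%, loss 6.8%, and 10% indeterminate for community ambulation at 40 weeks (Protocol 15.6.2, stated for other outcomes and borrowed here).
- The documents state no expected QALY gain, incremental cost or ICER.

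**1. The protocol's own figure.** Detectable difference = (1.960 + 0.842) × SD × √(2/n) / (1 − noncompliance).
- n = 75 × 0.932 = 69.9: 2.802 × 0.10 × √(2/69.9) / 0.878 = 0.054.
- n = 75 × 0.90 = 67.5: 2.802 × 0.10 × √(2/67.5) / 0.878 = 0.055.

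The figure reproduces as a difference in mean SF-6D score. It is a utility difference, not a QALY difference.

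**2. Units.** For a horizon of T years, area = T × (time-average of the difference). Hence average/area = 1/T. At 40 weeks, T = 40/52 = 0.769 and 1/T = 1.30.

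**3. Example.** Assume a difference of 0 at randomization and 0.055 at weeks 16 and 40, joined by straight lines.
- Utility-weeks: ½ × 16 × 0.055 + 24 × 0.055 = 0.44 + 1.32 = 1.76.
- Area: 1.76/52 = 0.034 QALY.
- Time-weighted average: 1.76/40 = 0.044.
- Ratio: 52/40 = 1.30.

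**4. If the baseline zero is left out.** The two follow-up effects would then be averaged with weights 16:24. The ratio now depends on the assumed pattern:

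| Difference at wk 16, wk 40 | Area (QALY) | Average with baseline zero (ratio) | 16:24 average without it (ratio) |
|---|---|---|---|
| 0.055, 0.055 | 0.0338 | 0.0440 (1.30) | 0.0550 (1.63) |
| 0.055, 0 | 0.0212 | 0.0275 (1.30) | 0.0220 (1.04) |
| 0, 0.055 | 0.0127 | 0.0165 (1.30) | 0.0330 (2.60) |

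**5. Effect on the ICER.** ICER = ΔCost/ΔQALY. Replacing ΔQALY by 1.30 × ΔQALY gives ICER/1.30, or 77% of its proper magnitude, whatever the cost.

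**The case against.** The best defence is that the sentence is loose rather than wrong. The weights are not given. If they are interval lengths in years, the result is the correct area. If the averaged quantities are QALYs per interval, as the label at each time point might suggest, averaging would understate the gain: (16 × 0.0085 + 24 × 0.0254)/40 = 0.019 against their sum of 0.034. The stated aim of QALYs over follow-up suggests that the authors meant an area.

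That defence counts against treating any one numerical error as certain. It does not rescue the wording. Weights in years sum to 40/52 = 0.77, which makes the result an area and not an average; and estimates at a time point are not interval totals. Each alternative needs a different sentence, and the SAP's introduction says that it adds detail so that the plan is fully specified.

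Several stronger readings are tempting, and the documents do not support them:
- **That the ICER is bound to be too favourable to PUSH.** This needs both a QALY gain and a higher cost. If PUSH gains QALYs and saves money, or loses QALYs and costs more, its dominance does not change. If it loses QALYs and saves money, the error works against it. Both arms are scheduled for 32 visits of about an hour, so the cost difference may be small.
- **That the error moves the ICER across a decision threshold.** In the example, the 50,000-dollar threshold of Protocol 15.6.2 is crossed only if incremental cost lies between 50,000 × 0.0338 = 1,690 dollars and 50,000 × 0.044 = 2,200 dollars. The documents give no cost.
- **That inflation reaches 52/16 = 3.25.** This needs a 16-week horizon. The protocol says "We estimate that there will be approximately 150 participants for whom the full 40-week follow-up will be available", and about 160 were expected to be randomized before SF-36 and utilization were dropped. That leaves about 10 participants with economic data to week 16 only.
- **That baseline is ignored.** SF-36 is measured at baseline, and SAP Eq. 2 has no treatment term at baseline, so the zero is available to the calculation. The text does not say whether it is used.
- **That incremental net benefit is biased.** It appears only in the protocol's power section; SAP 1.3 plans no such analysis.

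**Conclusion.** The concern holds for the rule as worded. Taken literally, it returns a mean utility difference labelled as QALYs. Over 40 weeks with baseline included, the magnitude of the QALY difference is overstated by 1.30, whether it is a gain or a loss, and the trial-based ICER is too small in magnitude by the same factor. If the baseline zero is left out, the factor rises to 1.63 when the effect is equal at both visits, and ranges from 1.04 to 2.60 over the patterns tried.

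These sizes assume weights that sum to one, a 40-week horizon, and linear change between visits; the effect patterns are illustrative. The direction of any bias for or against PUSH is not established. The consequence is confined to a secondary analysis that runs only if the SAP's condition is met, and reaches the model-based analysis only through the QALY inputs taken from the trial. The primary result is untouched. The correction is worth making because the ICER is the main economic output and the change costs nothing.

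**What to change.** In SAP 1.3 and Protocol 15.2.3:
- Call the time-point estimates SF-6D (utility) differences.
- Define incremental QALYs as the trapezoidal area under the PUSH-minus-PULSE SF-6D difference curve, with time in years, from zero at randomization through weeks 16 and 40. With d16 and d40 as the differences: (16/52) × d16/2 + (24/52) × (d16 + d40)/2.
- State the horizon and accumulate costs over the same horizon.
- State how participants followed for 16 weeks only contribute, since "Follow-up will end at 16 weeks post-randomization for those consented under version 10.0 of the protocol".

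This is a change of wording and of one formula. It needs no new data and no change to any other analysis. For a given cost difference, the reported cost per QALY would be 1.30 times larger in magnitude than under the literal 40-week average with baseline included.

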1.4 Missing Data

By design, there will be no missing data at baseline because only participants with complete baseline data will be randomized. At follow-up, scores for scales that have published rules for handling missing scale items (e.g., the CES-D and the SF-36) will be calculated using those rules. If necessary, the PAT-D and each of its subscales will be prorated based on nonmissing items. However, the whole scale will be considered missing if more than 30% of its items are missing. Similarly, each of the subscales will be missing if more than 30% of the subscale items are missing. If necessary, the mPPT will be prorated based on nonmissing items. However, the scale will be considered missing if three or more of the tasks were not done because of technical issues (e.g., no stairs available for stair climbing task). All other scales will be considered missing if any part of the scale is missing. As a secondary analysis, to correct for imbalances due to chance or differential missing data, we will adjust for covariates in our models. Candidate variables that will be adjusted for are age, sex, and type of hip fracture; baseline BMI, MNA[®]-SF score, CES-D score, 3MS score, distance walked in six minutes on SMWT, SPPB score, mPPT score, NHATS balance score, gait speed on 50-ft fast walk, and gait speed on 4-m usual walk; and the presence of cardiac disease, pulmonary disease, diabetes, and history of stroke or TIA at baseline. As described above, these variables will be ranked for inclusion as adjustment variables using the Beach-Meier approach (Beach 1989). We will adjust for the same number of covariates in this analysis as in the analysis described in

above for covariate adjustment for the analysis of our primary outcome. This approach will result in unbiased estimates if the missingness is at random, conditional on the covariates.

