Assessment of Effect Modification of site, period (pre and post decreased visit frequency) and patient characteristics. (Section 1.1.3)	No details provided	Additional Details: Effect modification will be tested on the risk-difference scale based on a binary regression model with an identity link. Also, baseline physical performance as measured by the SPPB will be tested as a potential effect modifier.
Model-based estimates of Delayed and Sustained Effects on Primary Outcome (Section 1.2.1)	Longitudinal logistic regression for two time points (baseline, 16-week, 40-week) model fit with GEE to account for repeated measures from same individual	Changed to a longitudinal binary regression model with identity link and random effect for subject to account for repeated measures. Rationale: Estimates interpretable as rate differences.
Subject-based estimates of delayed and sustained effects on Primary Outcome (Section 1.2.1)	Not in original plan	3x3 table in each treatment group with rows indicating community ambulation at 16 weeks (yes, no, indeterminate) and columns indicating community ambulation at 40 weeks (yes, no, indeterminate).
Secondary and Tertiary Outcomes		
Longitudinal Data Analysis of quantitative secondary and tertiary outcomes. (Section 1.2.2)	Longitudinal Analysis based on three time points (baseline, 16-weeks, and 40-weeks) fit by GEE.	Changed from GEE to maximum likelihood with an unstructured variance. Rationale: A little more flexible than GEE and may adjust for baseline values better.
Sensitivity analysis to account for missing outcome data (Section 1.4)	Weighted Estimating Equations	Adjustment for covariates in the longitudinal regression model. Covariates chosen by a published method
Sensitivity analysis for non-adherence to protocol (removed)	Weighted analysis with weights based on inverse probability of treatment received as a function of covariates and treatment	Not included in new plan due in part to difficulty defining adherence.
Sensitivity analyses to variation between physical therapists or sites (Section 1.5)	Not in original plan	Rerun the analyses including a random effect for physical therapist or site.

Section 1. Detailed Statistical Analysis Plan

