1.2.2 Secondary and Tertiary Outcomes

Secondary outcomes include five variables (endurance, dynamic balance, walking speed, quadriceps strength, and lower extremity function) that are hypothesized to be precursors to community ambulation. In addition, we will examine the difference between the treatments with respect to the following tertiary outcomes: ADLs, balance confidence, quality of life, physical activity, lower extremity physical performance, depressive symptoms, increase of ≥ 50 meters in distance walked in six minutes, cognitive status, and nutritional status.

With the exception of “increase of 50 meters in distance walked in six minutes”, these variables are quantitative. Prior to analyzing the relationship between treatment and the quantitative variables we will use histograms and side-by-side box plots to examine the shape of the distributions and identify potential outliers. If the data strongly depart from normality, we will consider transforming the data or using rank-based methods for the analyses described below.

Mixed effects models fit by restricted maximum likelihood will be used to compare the PUSH and PULSE interventions at 16 and 40 weeks post-randomization with respect to each outcome. Increase of ≥ 50 m in distance walked, a dichotomous outcome, will be analyzed using the same method as the primary outcome. All of the other secondary and tertiary outcomes are continuous; therefore, a normal model will be used to estimate the parameters in the following equation:

$$\mu_{ij} = b_0 + b_1 t_{16_{ij}} + b_2 t_{40_{ij}} + b_3 X_i t_{16_{ij}} + b_4 X_i t_{40_{ij}}, \quad (\text{Eq. 2})$$

where μ_{ij} is the mean of the j th outcome from the i th participant, X_i is the intervention indicator (1/0) variable; $t_{16_{ij}}$ and $t_{40_{ij}}$ are the 16- and 40-week follow-up time post-randomization indicators, respectively; and $X_i t_{16_{ij}}$ and $X_i t_{40_{ij}}$ are the intervention-by-time interaction variables.

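### SAP 1.4 adds baseline covariates to a model in which baseline is already a response, without excluding an outcome's own baseline or letting covariate slopes differ by time, so the fit can be undefined and the stated unbiasedness is not assured

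*SAP*

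**What the plan says.** SAP 1.2.2 analyses the continuous secondary and tertiary outcomes with Eq. 2: "Mixed effects models fit by restricted maximum likelihood", with baseline, week 16 and week 40 all on the left-hand side. The two arms share one baseline mean. On the covariance, "we will fit an unstructured variance/covariance matrix to the three time points". The reason given for the set-up is: "By treating the baseline value as an outcome, we quantify mean changes in the outcome relative to baseline levels".

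SAP 1.4 then adds: "As a secondary analysis, to correct for imbalances due to chance or differential missing data, we will adjust for covariates in our models". The SAP's table of changes from the protocol confirms which model is meant: "Adjustment for covariates in the longitudinal regression model. Covariates chosen by a published method". The candidates in 1.4 include "distance walked in six minutes on SMWT, SPPB score, mPPT score, NHATS balance score, gait speed on 50-ft fast walk" and, after the MNA prefix, "SF score, CES-D score, 3MS score". Candidates are ranked by the Beach-Meier approach. The number that enter is the number used in the weighting model of SAP 1.1.2, which allows one covariate per 10 events and 10 non-events. SAP 1.4 concludes: "This approach will result in unbiased estimates if the missingness is at random, conditional on the covariates".

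SAP 1.4 does not say that an outcome's own baseline is left out, that baseline leaves the response when covariates are added, or whether a covariate has one slope or a separate slope at each time.

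**The concern.** There are two gaps.

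- **Own baseline.** SMWT distance, NHATS balance, 50-ft walk, mPPT, SPPB, CES-D, 3MS and MNA-SF are each an Eq. 2 outcome and a candidate covariate. They are eight of the 13 continuous outcomes in SAP 1.2.2 and cover four of the five secondary outcomes. Four-metre gait speed would be a ninth, but it appears as an outcome only in SAP 1.3. For its own outcome such a covariate equals the time-0 response exactly.
- **Other covariates.** Read in the ordinary way, an added covariate has one slope for all three times. That slope is a compromise between its association with baseline and its association with follow-up, so it may under-adjust the follow-up means.

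At stake is the covariate-adjusted analysis that replaces the protocol's weighted estimating equations for these outcomes. It could fail to fit, forcing an unplanned choice after the data are seen, or it could be reported as corrected when it is only partly so.

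**Working it through.** **The plan's own figure.** The documents give no figure for the 1.4 adjustment. The nearest is the detectable effect in Protocol 15.6.2: 0.46 SD with N = 210, 6.8% loss, 12.2% nonadherence, two-sided 0.05 and 80% power. Per arm, n = 105 × (1 − 0.068) = 97.86, so d = (1.960 + 0.842) × √(2/97.86) / (1 − 0.122) = 0.4005/0.878 = 0.456. The figure reproduces and is not in dispute.

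**How many covariates enter.** With 16% and 36% ambulators (Protocol 15.6.1), events = 97.86 × (0.16 + 0.36) = 50.9, giving 5 of 17. Allowing for nonadherence gives 48.5 events and 4 covariates. Rates of 9%/29%, 23%/43% and 16%/16% give 3, 6 and 3.

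**Own baseline as an ordinary covariate.** Add γY₀ to the mean at all times. The residuals become (1 − γ)Y₀, Y₁₆ − γY₀ and Y₄₀ − γY₀, each less its mean. An unstructured covariance fits these as well as the original responses, apart from a scale factor of (1 − γ) per participant:

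logL(γ) = logL(0) − n·ln(1 − γ), which has no upper limit as γ → 1.

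- Profile run (simulated, n = 196, assumed SD 83 m and correlations 0.6/0.7): −3284 at γ = 0, −2381 at 0.99, −1478 at 0.9999. The formula predicts steps of 196 × ln 100 = 903, as found. The week-16 contrast b3 stays at 25.13 (SE 8.37), because E(Y₀) does not depend on arm.
- Separate run (N = 210), reducing the baseline residual variance from 1 to 10⁻⁶: ML rises from −542 to 893 and REML from −558 to 864. Once the variance is small, each tenfold fall adds about 210/2 × ln 10 = 242 to ML.

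**Own baseline at follow-up times only.** The scale factor is now 1, so the likelihood is flat. LogL is −627.3809 for every split tried between the coefficient and the baseline covariance, with treatment contrasts fixed at 0.115 and 0.055.

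**Other covariates.** Assumed, because the documents do not give them: baseline/week-16 correlation ρ of 0.5–0.8, and covariate effects g₀ on baseline and g₁ on week 16, with r = g₀/g₁. Eq. 2 without covariates leaves a covariate effect of g₁ − ρg₀. With equal variances the shared slope is about (g₀ + g₁)/2 and absorbs (1 − ρ) times that, so

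share of bias left = 1 − (1 − ρ)(1 + r) / [2(1 − ρr)].

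| r | ρ = 0.5 | ρ = 0.7 | ρ = 0.8 |
|---|---|---|---|
| 0 | 0.75 | 0.85 | 0.90 |
| 0.5 | 0.50 | 0.65 | 0.75 |
| 0.8 | 0.25 | 0.39 | 0.50 |
| 1 | 0 | 0 | 0 |

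More than half is left only when r < ρ. Large-sample simulation (N = 400,000) gave 77%, 85% and 91% at r = 0, and 52%, 64% and 77% at r = 0.5. A further run at about 7.6% missing gave 75–83%, 56–66% and about 0% for r = 0, 0.5 and 1.

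**Absolute size.** Assume 6.8% loss per arm, a binary covariate with prevalence 0.3, and loss only among carriers in PUSH and only among non-carriers in PULSE. Observed prevalences are (0.3 − 0.068)/0.932 = 0.249 and 0.3/0.932 = 0.322, a gap of 0.073. With g₁ = 0.5 SD and r = 0, the unadjusted bias is 0.073 × 0.5 = 0.037 SD (simulated 0.035–0.042). A main effect leaves 0.029–0.038 SD in the simulation. Covariate-by-time terms leave about 0, within 0.004 SD simulation error, in all 12 scenarios.

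In metres, at 8.5% missing and SD 83 m, bias was 5.4 unadjusted, 4.3 with a main effect and 0.2 by time (effects 0 and 30 m per SD), and 4.9, 2.9 and −0.3 (effects 15 and 40 m). The main-effect remainders are 4.3/83 = 0.05 and 2.9/83 = 0.03 SD. As a stress case, 20% loss gave 0.12, 0.11 and about 0 SD.

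**The case against.** The strongest reply is that this is a secondary analysis on top of a sound one. Eq. 2 is a likelihood model with unstructured covariance that uses every observed baseline and follow-up value. It is valid when missingness is at random given those values. That stands, and it rules out the reading that SAP 1.4 is the only protection against missing data for these outcomes.

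A reader might also infer that the model has no maximum for all eight outcomes. The documents do not support that. Candidates are ranked and only about 3 to 6 enter. If one ranked list serves every outcome, at most about six could be affected. If ranking is repeated per outcome, the count depends on a criterion the SAP cites but does not describe. Eight is the number exposed.

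A reader might further infer that the other covariates leave most of the missing-data bias in place. That needs a shared slope, which the SAP does not state, and a covariate with r below ρ. It also needs missingness that runs differently in the two arms; with the same pattern in both, the bias in the contrast largely cancels. Several candidates, such as SPPB and gait speed, probably relate to baseline walking distance as well as to follow-up.

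Finally, an own-baseline failure would be visible or harmless, because the contrast does not move. This is true, but an adjustment that cannot be fitted or changes nothing is not the analysis the SAP promises.

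**Conclusion.** The point holds in conditional form. For any of the eight exposed outcomes whose own baseline is selected, an ordinary covariate term makes the ML or REML criterion unbounded; a follow-up-only term is not identified and adjusts nothing. This is algebra and rests on no assumed input. For other covariates, the claim of unbiasedness under missingness at random is not assured as written: a shared slope delivers it fully only when r = 1, whereas covariate-by-time slopes removed the bias in every scenario run.

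The size of the second part rests on assumed correlations, covariate effects and arm-specific missingness. At 7–8% loss it is about 0.04–0.06 SD or less, against a detectable effect of 0.46 SD. In metres, the remainders of 2.9–4.3 m compare with the 50 m that SAP 1.3 calls clinically meaningful. The primary analysis and unadjusted Eq. 2 are not affected. The change is worth making because it costs little and removes a choice that would otherwise be made with the data in hand.

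**What to change.** In SAP 1.4:

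1. For each outcome, remove its own baseline value from the candidate list, because Eq. 2 already uses it as a response.
2. Enter every selected covariate with covariate-by-t16 and covariate-by-t40 terms in addition to its main effect.

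The second change does not replace the first: an own baseline with a term at baseline still gives an unbounded criterion. If baseline is instead moved out of the response, the baseline value and the covariates should each have separate slopes at weeks 16 and 40; otherwise the shared-slope restriction returns.

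The cost is two more parameters per covariate (ten with five covariates), two sentences in the SAP and a small programming change. No new data are needed.
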